7.2 DATA DISCLOSURE

Information will not be disclosed to anyone outside of the study team.

7.3 DATA SAFETY AND MONITORING

All data will be stored on secured Tennessee Oncology servers and all files will be password protected.

7.4 SOURCE DATA DOCUMENTATION

Tennessee Oncology monitor(s) will perform ongoing source data verification to confirm that critical protocol data (i.e., source data) entered into the Electronic Medical Record (EMR) by authorized site personnel are accurate, complete, and verifiable from source documents.

Source documents (paper or electronic) are those in which patient data are recorded and documented for the first time. They include, but are not limited to, hospital records, clinical and office charts, laboratory notes, memoranda, patient-reported outcomes, evaluation checklists, pharmacy dispensing records, recorded data from automated instruments, copies of transcriptions that are certified after verification as being accurate and complete, microfiche, photographic negatives, microfilm or magnetic media, radiology reports, patient files, and records kept at pharmacies, laboratories, and medico-technical departments involved in a clinical trial.

Confidential

Before study initiation, the types of source documents that are to be generated will be clearly defined in the Trial Monitoring Plan. This includes any protocol data to be entered directly into the EMR (i.e., no prior written or electronic record of the data) and considered source data.

Source documents that are required to verify the validity and completeness of data entered into the EMR must not be obliterated or destroyed and must be retained per the policy for retention of records described in Section 7.6.

To facilitate source data verification, the investigators and institutions must provide University of Pennsylvania direct access to applicable source documents and reports for trial-related monitoring, audits, and IRB/EC review. The clinics must also allow inspection by applicable health authorities.

7.5 USE OF COMPUTERIZED SYSTEMS

When clinical observations are entered directly into the clinic's computerized medical record system (i.e., in lieu of original hardcopy records), the electronic record can serve as the source document if the system has been validated in accordance with health authority requirements pertaining to computerized systems used in clinical research. An acceptable computerized data collection system allows preservation of the original entry of data. If original data are modified, the system should maintain a viewable audit trail that shows the original data as well as the reason for the change, name of the person making the change, and date of the change.

All Tennessee Oncology users and any use of any IT resource(s) are required to read and understand our data transmission security policy and procedure.

The purpose of our Data Transmission Security Policy and Procedures is to guard against unauthorized access to electronic protected health information that is being transmitted over an electronic communications network. The establishment and implementation of effective Data Transmission Security Procedures is a crucial element in our overall objective of providing reasonable protections for individually identifiable health information, including Protected Health Information ("PHI", as defined by HIPAA).

7.6 RETENTION OF RECORDS

Records and documents pertaining to the conduct of this study and the distribution of data, including EMR, paper PRO data (if applicable), Informed Consent Forms, laboratory test results, and medication inventory records must be retained by the Principal Investigator for at least 15 years after completion or discontinuation of the study, or for the length of time required by relevant national or local health authorities, whichever is longer. After that period of time, the documents may be destroyed, subject to local regulations.

The research team will destroy audio-recordings 18 months after the study is complete. All data will be de-identified when stored. We will destroy all data 18 months after the study is complete.

No records may be disposed of without the written approval of Tennessee Oncology. Written notification should be provided to Tennessee Oncology prior to transferring any records to another party or moving them to another location.

8. ETHICAL CONSIDERATIONS

8.1 COMPLIANCE WITH LAWS AND REGULATIONS

This study will be conducted in full conformance with the ICH E6 guideline for Good Clinical Practice and the principles of the Declaration of Helsinki, or the laws and regulations of the country in which the research is conducted, whichever affords the greater protection to the individual. The study will comply with the requirements of the ICH E2A guideline (Clinical Safety Data Management: Definitions and Standards for Expedited Reporting).

8.2 REVIEW BOARDS & ETHICS COMMITTEE

As required by local regulations, the Investigator will ensure approval of the appropriate regulatory bodies is obtained, prior to study initiation. If required, the Investigator will also ensure that the implementation of substantial amendment to the protocol and other relevant study documents happen only after approval by the relevant regulatory authorities.

The Advarra Institutional Review Board (IRB) will review Tennessee Oncology's research activities. The Advarra IRB is an independent IRB that provides services for academic and non-academic institutions. The study protocol will also be submitted to the University of Pennsylvania IRB for review.

8.3 INFORMED CONSENT

For administering quality of life and communication questionnaires, we request a verbal consent process. This is requested since our intervention will be being conducted via telephone and with the large geographic distribution of our practice (over 130 miles between clinics), it would not be feasible to obtain written consent for the questionnaire component of the study for patients. An information form will be read to the patient and mailed to them if they consent to completing the questionnaire via telephone.

For the intervention itself, a waiver of informed consent is requested. This is a health system initiative that will be implemented. The study is to evaluate that initiative. Therefore, physicians and their patients will not be consented as this is the standard of practice per the health system initiative. Without a waiver of the consent, the initiative would still be implemented by the health system, but the study would be infeasible. There are several additional reasons why we feel a waiver of consent should be granted. First, it is not feasible to consent every physician and as mentioned this initiative would occur with or without the study of it. Second, if members of the control group were consented, this alone could change their behavior. This could potentially disrupt the design of the study and making interpretation of the findings challenging. Third, physicians are not being forced to refer patients to palliative care. This intervention decreases the cognitive burden of remembering which patients are appropriate and would benefit from palliative care. The oncologist always retains control of the referral by being able to "opt-out" and cancel the referral on a case by case basis. This intervention is working towards better implementation of what is considered standard of care for patients with advanced care.

Verbal consent will be obtained from each clinician who participates in the semi-structured interviews (see **Exhibit 7**). Written consent is not necessary for this part of the project because clinicians will not be required to participate and can opt out at any point. No patient identifying information will be provided to clinicians.

8.4 CONFIDENTIALITY

Tennessee Oncology maintains confidentiality standards by coding each patient enrolled in the study through assignment of a unique patient identification number. This means that patient names are not included in data sets that may be transmitted.

All efforts will be made by study staff to ensure subject privacy. Data will be evaluated in a de-identified manner whenever possible. All transcripts will be de-identified and stored in password protected files on a secure folder at Tennessee Oncology.

Computer-based files will only be made available to personnel involved in the study using access privileges and passwords. Wherever feasible, identifiers will be removed from study-related information. Precautions are already in place to ensure the data are secure by using passwords and HIPAA-compliant encryption.

Patient medical information obtained by this study is confidential and may only be disclosed to Tennessee Oncology trained study staff. Electronic data will be stored on secure, password-protected firewalled servers.

Data generated by this study must be available for inspection upon request by representatives of the U.S. FDA and other national and local health authorities, representatives, and collaborators, and the IRB/EC for each study site, as appropriate.

The research team at the University of Pennsylvania will not have access to identifiable information in this trial. All data for this project will be stored on the secure/firewalled servers of the DART system, in data files that will be protected by multiple password layers. These data servers are maintained in a guarded facility behind several locked doors, with very limited physical access rights. They are also cyber-protected by extensive firewalls and multiple layers of communication encryption. Electronic access rights are carefully controlled by University of Pennsylvania system managers. We believe this multi-layer system of data security, identical to the system protecting the University of Pennsylvania Health Systems medical records, greatly minimizes the risk of loss of privacy. In addition, risk of loss of confidentiality will be minimized by storing completed paper copies of the surveys and signed informed consent forms in locked file cabinets in locked offices accessible only to trained study staff. Each subject will be assigned a unique identifier without identifying information, and data will be entered into an electronic database using only the unique identifier. Only trained study staff will have access to the code that links the unique identifier to the subject's identity. Electronic data will be stored on secure, password-protected firewalled servers at the University of Pennsylvania.

9. STUDY DOCUMENTATION, MONITORING, AND ADMINISTRATION

9.1 STUDY DOCUMENTATION

The investigator must maintain adequate and accurate records to enable the conduct of the study to be fully documented, including but not limited to the protocol, protocol amendments, and documentation of IRB/EC and governmental approval when applicable. In addition, at the end of the study the investigation will receive the patient data, which includes an audit trail containing a complete record of all changes to data.

9.2 PROTOCOL DEVIATIONS

The investigator should document and explain any protocol deviations. The investigator should promptly report any deviations that might impact study patient data integrity to the IRB/EC in accordance with established IRB/EC policies. As per Tennessee Oncology's standard operating procedures, perspective to deviate from the protocol, including requests to waive protocol eligibility criteria are not allowed.

9.3 CLINIC INSPECTIONS

Clinic visits will be conducted by Tennessee Oncology or an authorized representative for inspection of study data, patients' medical records, and source documentation. The investigator will permit national and local authorities, collaborators, and the IRBs/ECs to inspect facilities and records relevant to this study.

9.4 ADMINISTRATIVE STRUCTURE

The study is sponsored by Tennessee Oncology, PLLC and University of Pennsylvania. Tennessee Oncology Research Team will perform study and safety monitoring, data collection and management. Data analysis and dissemination of study findings including publication will be in collaboration with research team led by [name] at University of Pennsylvania.

9.5 PUBLICATION OF DATA AND PROTECTION OF TRADE SECRETS

Regardless of the outcome of a trial, Tennessee Oncology is dedicated to openly providing information on the trial to healthcare professionals and to the public, both at scientific congresses and in peer-reviewed journals. Tennessee Oncology will comply with all requirements for publication of study results.

In accordance with standard editorial and ethical practice, Tennessee Oncology will support publication of multi-centers only in their entirety and not as an individual center data.

9.6 PROTOCOL AMENDMENTS

Any protocol amendments will be prepared by Tennessee Oncology. Protocol amendments will be submitted to the IRB/IEC and to regulatory authorities in accordance with local regulatory authorities.

A protocol amendment will be provided if data inclusion/exclusion criteria has been added to the study.

Approval will be obtained from the IRB/IEC and regulatory authorities (as locally required) before implementation of any changes, except for changes necessary to eliminate an immediate hazard to the patients or changes that involve logistical or administrative aspects only.

Bone Metastases in Diagnosis List or Charge	If exists	1	1
Secondary malignant neoplasm of brain	If exists	1	1
COPD in diagnosis list or charge	If exists	1	1
CHF in diagnosis list or charge	If exists	1	1
Dementia in Diagnosis List or Charge	If exists	1	1
Liver Cirrhosis in diagnosis list or charge	If exists	1	1
Stroke in diagnosis list or charge	If exists	1	1
Spinal cord compression in Diagnosis list or charge	If exists	1	1
Most recent NCCN Distress Score	≥ 8	1	1
Most recent ECOG Performance Score	≥ 2	1	1
Most recent PHQ-2 Score	≥ 3	1	1
Number of ED visits in prior 3 months	Each ED visit receives 2 points	1	2
Number of Inpatient stays in prior 3 months	Each Inpatient stay receives 2 points	1	2
Low Age	<40	1	1
High Age	≥ 70	1	1

Total Risk Score	Interpretation	Time to Palliative Care Visit
>1 Stage IV, >2 Stage III	High Risk	2 weeks
<1 Stage IV, <2 Stage III	Non-High Risk	4 weeks

EXHIBIT 2

[figure not shown]
Exhibit 2. Trial Schema

*Score ≥ 1 Stage IV, ≥ 2 Stage III – high risk on algorithm

EXHIBIT 3

Exhibit 3. Organizational Structure

*Panelists with expertise in machine learning, informatics, palliative care, and cancer care delivery. As per NIH guidance, we do not name panel members in this application so as not to preclude reviewers from their academic institutions.

EXHIBIT 4

Patient Surveys

FEELING HEARD AND UNDERSTOOD

Individuals can respond to each data element using discrete values ranging from 1 (Completely true) to 5 (Not at all true.)

Q1. I felt heard and understood by this provider and team.

- | | | | | |
|--------------------|--------------|-------------------|-----------------------|---------------------|
| 1. Completely true | 2. Very true | 3. Somewhat true. | 4. A little bit true. | 5. Not at all true. |
|--------------------|--------------|-------------------|-----------------------|---------------------|

Q2. I felt this provider and team put my best interests first when making recommendations about my care.

- | | | | | |
|--------------------|--------------|-------------------|-----------------------|---------------------|
| 1. Completely true | 2. Very true | 3. Somewhat true. | 4. A little bit true. | 5. Not at all true. |
|--------------------|--------------|-------------------|-----------------------|---------------------|

Q3. I felt this provider and team saw me as a person, not just someone with a medical problem.

- | | | | | |
|--------------------|--------------|-------------------|-----------------------|---------------------|
| 1. Completely true | 2. Very true | 3. Somewhat true. | 4. A little bit true. | 5. Not at all true. |
|--------------------|--------------|-------------------|-----------------------|---------------------|

Q4. I felt this provider and team understood what is important to me in my life.

- | | | | | |
|--------------------|--------------|-------------------|-----------------------|---------------------|
| 1. Completely true | 2. Very true | 3. Somewhat true. | 4. A little bit true. | 5. Not at all true. |
|--------------------|--------------|-------------------|-----------------------|---------------------|

FACIT-PAL 14

Below is a list of statements that other people with your illness have said are important. **Please circle or mark one number per line to indicate your response as it applies to the past 7 days.**

		Not at all	A little bit	Some-what	Quite a bit	Very much
GP1	I have a lack of energy	0	1	2	3	4
GP2	I have nausea	0	1	2	3	4
GP4	I have pain	0	1	2	3	4
GE6	I worry that my condition will get worse	0	1	2	3	4
GF3	I am able to enjoy life	0	1	2	3	4
GF5	I am sleeping well	0	1	2	3	4
GF7	I am content with the quality of my life right now	0	1	2	3	4
GS2	I get emotional support from my family	0	1	2	3	4
Sp21	I feel hopeful	0	1	2	3	4
GE1	I feel sad	0	1	2	3	4
Pal4	I feel like a burden to my family	0	1	2	3	4
Pal5	I am constipated	0	1	2	3	4
Pal14	I am able to openly discuss my concerns with the people closest to me	0	1	2	3	4
B1	I have been short of breath	0	1	2	3	4

EXHIBIT 5

EHR notification with option to opt-out

Subject: Patient eligible for palliative care referral

Tennessee Oncology is committed to offering palliative care to patients with advanced cancer.

Mr./Mrs.____ is eligible for palliative care referral due to _____ (include risk factors that flagged them here).

If you agree with palliative care consultation, there is no need to reply. After 48 hours, we will proceed with calling, introducing and offering palliative care to the patient using a validated script. Your patient will have the opportunity to ask questions about palliative care and to decline.

If you DO NOT wish to proceed with palliative care referral, please reply "Opt-Out". If you opt-out, please indicate why from the following choices:

- I have already referred to palliative care.
- I wish to discuss this with my patient first.
- I do not believe this patient's disease or clinical factors warrant palliative care.
- I worry about the patient getting the wrong message with our treatment goals.
- Other – please explain

Sincerely,

[name]

[name]

[name]

EXHIBIT 6

Recruitment Emails for Oncology and Palliative Care Clinicians

Recruitment Email for Oncology Clinicians

Subject: Re: your feedback on upenn palliative care study

Dear Dr. ___ or NP name,

We have completed enrollment for our palliative care clinical trial with University of Pennsylvania and would love your **feedback on being a participant in the intervention group.**

This is a separate qualitative study where you will be interviewed, and your feedback will be incorporated to improve our model for palliative care referrals among patients with advanced lung and non-colorectal GI malignancies.

We are offering a \$100 gift card for your time and participation.

Let me know when a good time for us to meet and conduct the interview for approximately 30 minutes. I can meet with you in person (for middle TN), virtually (zoom or skype), or via telephone.

Thank you for your time and consideration.

Sincerely,
[name]

Recruitment Email for Palliative Care Clinicians

Subject: Re: your feedback on upenn palliative care study

Dear Dr. ___ or NP name,

We have completed enrollment for our palliative care clinical trial with University of Pennsylvania and would love your **feedback on being a palliative care clinician in this study.**

This is a separate qualitative study where you will be interviewed, and your feedback will be incorporated to improve our model for palliative care referrals among patients with advanced lung and non-colorectal GI malignancies.

We are offering a \$100 gift card for your time and participation.

Let me know when a good time for us to meet and conduct the interview for approximately 30 minutes. I can meet with you in person (for middle TN), virtually (zoom or skype), or via telephone.

Thank you for your time and consideration.

Sincerely,
[name]

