3.2 PRIMARY OUTCOME

Completed palliative care visit within 3 months among high-risk patients with stage III and IV lung and non-colorectal GI malignancies

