4.6 INTERVENTIONS

Clinicians of patients in both arms will receive education on the availability of early palliative care and performance reports. Clinicians in Arm 1 (intervention) will receive a EHR notification with option to opt-out (placed by the research coordinator, see **Exhibit 5**) for palliative care referral for any eligible high-risk patient, defined by a risk score ≥ 1 for Stage IV cancer patients and ≥ 2 for Stage III cancer patients. If the risk score is above 8, they will be scheduled within 2 weeks, and all other patients will be scheduled within 4 weeks. Clinician will have the option to opt-out for any patient by responding to the notification which will be sent to the research coordinator. If the clinician does not respond, the research coordinator will approach patient via telephone, explain the rationale for referral based on a predetermined script, and offer and schedule an outpatient or telemedicine palliative care consultation per patient preference. Follow-up visits will occur at the discretion of the palliative care clinician, usually monthly. Clinicians in both arms will receive monthly peer comparison emails that compare their palliative care referral rates against other clinicians.

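### The high-risk cut is ≥1/≥2 in section 4.6 and Exhibit 2 but >1/>2 in Exhibit 1, so patients exactly on the cut fall in neither Exhibit 1 group

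*Combined protocol and SAP*

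**What the plan says.** The high-risk cut appears in three places.

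- **Section 4.6 (Interventions):** high-risk is "defined by a risk score ≥ 1 for Stage IV cancer patients and ≥ 2 for Stage III cancer patients".
- **Exhibit 2 (Trial Schema), footnote:** "Score ≥ 1 Stage IV, ≥ 2 Stage III – high risk on algorithm".
- **Exhibit 1 (Risk Algorithm), interpretation table:** the High Risk row reads ">1 Stage IV, >2 Stage III" and the Non-High Risk row reads "<1 Stage IV, <2 Stage III". No row covers equality.

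Section 4.5 cites Exhibit 1 when it says that weekly runs of the algorithm will identify high-risk patients.

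The label carries the main outcomes. Section 3.2 gives the primary outcome as "Completed palliative care visit within 3 months among high-risk patients with stage III and IV lung and non-colorectal GI malignancies". Sections 3.3 and 6.4 set the secondary outcome, completed palliative care visits, in non-high-risk patients.

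**The concern.** High-risk status does three jobs here. It triggers the default referral in the intervention arm, it defines the primary denominator in both arms, and its complement defines the secondary population. A threshold with that role should have one reading.

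As the text stands, someone programming from section 4.6 and someone programming from Exhibit 1 would treat a patient exactly on the cut differently. The Exhibit 1 version also leaves such a patient unclassified. No passage says which statement prevails.

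The point concerns membership of the analysis populations, not the timing of visits.

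**Working it through.** **Step 1: can a score land exactly on the cut?** Every item in Exhibit 1 adds a whole number of points. Single factors add 1, for example "Bone Metastases in Diagnosis List or Charge". Emergency visits add 2 ("Each ED visit receives 2 points"), and inpatient stays are scored in the same way. Totals are therefore integers, and both boundary values occur in ordinary cases:

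- Stage IV with bone metastases and nothing else: total 1.
- Stage IV, aged 70 or over, with nothing else: total 1.
- Stage III with one emergency visit and nothing else: total 2.

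**Step 2: classify each score under both rules.**

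| Stage | Score | Section 4.6 and Exhibit 2 | Exhibit 1 as printed |
|---|---|---|---|
| IV | 0 | non-high-risk | non-high-risk |
| IV | 1 | high-risk | neither row |
| IV | 2 or more | high-risk | high-risk |
| III | 0 or 1 | non-high-risk | non-high-risk |
| III | 2 | high-risk | neither row |
| III | 3 or more | high-risk | high-risk |

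The two definitions differ in exactly two cells: Stage IV with score 1 and Stage III with score 2.

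**Step 3: follow those two cells into the outcomes.**

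- Under section 4.6 and Exhibit 2, they are in the primary population, and those in the intervention arm are nudged.
- Under Exhibit 1 as printed, they are in neither the primary nor the secondary population.
- If a programmer used the upper row of Exhibit 1 and treated everyone else as non-high-risk, they would move to the secondary population.

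**Step 4: look for a count.** Section 6.5 takes about 4000 eligible encounters and a flag rate of 8-10%. That gives 4000 × 0.08 = 320 to 4000 × 0.10 = 400, and the planned 360 is 4000 × 0.09. The section does not say which cut produced the 8-10%. The documents give no prevalence for any risk factor and no distribution of scores. The number of patients on the boundary therefore cannot be derived.

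**Step 5: does the sample-size formula depend on this?** No. With 26.9% against 41.9%, two-sided alpha 0.05 and 80% power, the pooled two-proportion formula gives 157 per arm. Allowing for dropout, 157 / 0.90 = 174.4, so 175 per arm and 350 in total, against 360 planned. This treats patients as independent. The cut affects who counts towards the 360, not the formula behind it.

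**The case against.** The best defence is that the intended rule can largely be read from the page. The lower row of Exhibit 1 is the exact complement of ≥1/≥2, not of >1/>2. Three of four statements therefore fit one rule, and one pair of symbols is out of line. That pair could be a typing slip, or underlined signs that lost their underline when the PDF was read. The ≥ sign does survive elsewhere in Exhibit 1 (≥ 8, ≥ 2, ≥ 3, ≥ 70), which weakens the second explanation. Those entries are set differently, with a space after the sign, so it cannot be excluded. This part of the defence stands as a caution about the source. It does not remove the conflict in the text as it reads, and Exhibit 1 is the exhibit that section 4.5 cites for the weekly runs.

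It is also fair to say that the harm is conditional. Sections 4.1 and 4.5 describe weekly runs of one algorithm. A reader might infer that the nudge and the analysis data will follow different cuts. The documents describe no second data pull, so that remains a possibility and not a finding.

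A reader might also infer that the boundary group is large and that power would fall badly without it. The documents do not support a figure. Any estimate needs assumed factor prevalences, and plausible-looking values sit badly with the plan's flag rate. For example, assume independent factors with age 70 or over in 20%, an emergency visit in 5%, an inpatient stay in 5% and every other factor at zero. The ≥ rule then flags:

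- Stage IV: 1 − 0.80 × 0.95 × 0.95 = 27.8%.
- Stage III: 1 − 0.95 × 0.95 = 9.75%.
- With half the pool Stage IV: 0.5 × 27.8 + 0.5 × 9.75 = 18.8%.
- With 90% Stage IV: 0.9 × 27.8 + 0.1 × 9.75 = 26.0%.

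Both exceed 8-10%, although the comparison itself presumes that the ≥ rule produced that rate. Independence is doubtful too, since emergency visits, admissions and poor performance status plausibly cluster. This does not show that the group is small. It shows that its size is unknown.

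**Conclusion.** Wrong as written. The text gives two incompatible cuts for the label that selects nudged patients and defines the primary and secondary populations, and one version leaves a gap at equality. The extent is exact in terms of scores: two cells, Stage IV with score 1 and Stage III with score 2, with all other scores unaffected. No number or percentage of patients can be given, and no loss of power is claimed.

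The conclusion rests on the symbols as they read in the available text, so the source document should be checked for a lost underline. If the underline is there, only the explicit statement on populations and the code check remain to be done. Nothing here says which cut is right.

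**What to change.** 1. Check the High Risk row of Exhibit 1 in the source document.
2. Reconcile section 4.6, the Exhibit 1 interpretation table and the Exhibit 2 footnote to one inequality, written so that every whole-number score for each stage falls in exactly one row. The sponsor must decide which cut is intended.
3. Confirm that this is the rule coded in the weekly run.
4. State in section 6.4 that the same rule, applied identically in both arms, defines the primary (high-risk) and secondary (non-high-risk) populations.
5. Say in section 6.5 which cut produced the 8-10% flag rate.

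The cost is a wording correction and a check of the code, with no added patients or procedures.
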